10 STATISTICAL PROCEDURES

10.1 ANALYSIS VARIABLES

A statistical analysis plan (SAP), providing details of the analyses and presentation structure of the results, will be developed and finalized before the database is locked.

10.2 ANALYSIS POPULATIONS

Samples from all patients who complete the clinical study period will be assayed.

Dropouts will be replaced as described in section 9.1.

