3 STUDY DESIGN, DURATION AND DATES

3.1 STUDY DESIGN

This is a single center prospective cohort study that will assess the effect of Cycloset in in T2DM subjects who are inadequately controlled (HbA1c 7.5% to 10.0%) on GLP-1 analog therapy with either Bydureon (exenatide once weekly) or Victoza (liraglutide).

Subjects who meet the entry criteria will first undergo non-invasive hemodynamic testing for a baseline assessment of aortic compliance (Visit 1). Subjects will then come to the Clinical Research Center (CRC) at the Texas Diabetes Institute on the morning of Visit 2 following a 10-12 hour overnight fast and restriction from use of caffeine, tobacco, vitamins or medications that might affect vascular tone. Subjects will take their normal dose of exenatide or liraglutide in the

morning prior to this visit. At this visit, subjects will a non-invasive assessment of endothelial function using the Endo-PAT 2000 device Subjects will then receive a 5-hour MMT test. At approximately 90 minutes into the completion of the MMT test, a second Endo-PAT recording will be conducted. Upon completion of the second Endo-PAT test, subjects will be placed on a continuous ambulatory BP monitor and asked to collect a 24 hour urine sample, which they will start the following morning. After completion of the 24-hour urine collection, subjects will return to the CRC for Visit 3. At this visit, the ambulatory BP data will be downloaded and the 24-hr urine sample will be stored. Subjects will also have a DXA scan performed for assessment of body weight composition and have blood samples drawn for the measurement of serum cytokines and inflammatory biomarkers and isolation of white blood cells at this visit.

At Visit 3 subjects will be started on Cycloset, 0.8 mg/day in addition to their stable dose of Bydureon (exenatide) (2mg/week) or Victoza (liraglutide) (1.2-1.8 mg/day). Subjects will receive their first dose of Cycloset in the CRC and will be monitored for one hour after the dose before being sent home. The Cycloset dose will then be increased by 0.8 mg/day every week to a maximum of 3.2 mg/day, or as tolerated to a minimum of 2.4 mg/day. During the Cycloset titration phase subjects will be monitored by phone with weekly phone visits. Subjects who cannot tolerate at least 2.4 mg/day of Cycloset will be replaced.

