9 WITHDRAWALS

9.1 WITHDRAWAL OF SUBJECTS

Subjects may be withdrawn from the study (i.e. from any further study medication or study procedure) for the following reasons:

- At their own request or at the request of their legally authorized representative*
- If, in the investigator's opinion, continuation in the study would be detrimental to the subject's well-being
- · At the specific request of the sponsor
- * "Legally authorized representative" means an individual or judicial or other body authorized under applicable law to consent on behalf of a prospective subject to the subject's participation in the procedure(s) involved in the research.

Subjects must be withdrawn from the investigational product under the following circumstances:

- · Women who become pregnant
- Women of childbearing potential who discontinue contraception with the intention of becoming pregnant.

In all cases, the reason for and date of withdrawal must be recorded in the case report form and in the subject's medical records. The subject must be followed up to establish whether the reason was an adverse event, and, if so, this must be reported in accordance with the procedures in Section 8.

The investigator must make every effort to contact subjects lost to follow-up. Attempts to contact such subjects must be documented in the subject's records (e.g., times and dates of attempted telephone contact, receipt for sending a registered letter).

Subject withdrawal due to deterioration of glycemic control

Subjects with 2 consecutive fasting blood glucose values >275 mg/dl after completion of the study drug titration phase will be evaluated for withdrawal and initiation of rescue therapy at the discretion of the study investigators. Subjects that are withdrawn will be referred to their primary care physician or endocrinologist for further diabetes medication adjustments as needed.

Replacement of subjects

Subjects that are withdrawn within <2 months following completion of study drug titration will be replaced. As far as possible, for subjects who complete at least 2 months on a stable dose of the study drug following the study drug titration phase, all examinations scheduled for the final study day will be performed prior to withdrawal. Subjects who complete at least 2 months on a stable dose of the study drug following the study drug titration phase but are unable to complete the final study day procedures will also be replaced.

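### Section 10.2 does not say how HbA1c from replaced subjects is used, and the replacement rules point toward a completer mean, which overstates the reduction if non-completers do worse

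*Combined protocol and SAP*

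**What the plan says.** Section 10.2 (Analysis Populations) consists of two sentences: "Samples from all patients who complete the clinical study period will be assayed" and "Dropouts will be replaced as described in section 9.1". It defines no efficacy set and no missing-data rule. Section 10.1 leaves the analysis details to a SAP that "will be developed and finalized before the database is locked"; no such SAP is in the text available.

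Three groups are replaced:

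- Intolerance (section 3.1): "Subjects who cannot tolerate at least 2.4 mg/day of Cycloset will be replaced".
- Early withdrawal (section 9.1): "Subjects that are withdrawn within <2 months following completion of study drug titration will be replaced".
- Later withdrawal, after at least 2 months on a stable dose (section 9.1): those who reach that point "but are unable to complete the final study day procedures will also be replaced".

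Section 9.1 softens the third rule. After 2 months on a stable dose, and as far as possible, "all examinations scheduled for the final study day will be performed prior to withdrawal". It also links withdrawal to glycaemia: subjects with two consecutive fasting values above 275 mg/dl after titration "will be evaluated for withdrawal and initiation of rescue therapy at the discretion of the study investigators".

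HbA1c is drawn at months 1, 2 and 3 (sections 7.2.2.7 to 7.2.2.9) and again at Visits 7 and 8. The mixed meal test is scheduled only at Visits 2 and 7. Section 9.1 requires the reason and date of withdrawal to be recorded, and section 13.1 asks for missing data to be explained. Neither commits the report to showing them.

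**The concern.** Every subject receives Cycloset (section 5.1), so the mean change from baseline is itself the reported effect. Any selection of who enters that mean goes straight into the estimate, with no comparator in which it could cancel.

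The replacement rules select on tolerability and, through discretionary withdrawal for high fasting glucose, possibly on the outcome. Topping up to 15 also means that the final sample size need not reveal how many dosed subjects left. If those subjects did worse than the completers, a mean over the final 15 is too favourable, and nothing in the plan obliges the report to show by how much. Some of the excluded subjects would already have given usable HbA1c samples.

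**Working it through.** **1. The plan's own figure.** Section 10.3 gives a difference of 0.6, SD 0.5 (attached to baseline HbA1c), alpha 0.05, 90% power and 15 subjects. The two-sided two-sample normal formula gives n = 2 x (1.960 + 1.282)^2 x 0.5^2 / 0.6^2 = 14.6, so 15. The figure reproduces and is not disputed here. The SD of the change is not given. In a two-sided paired t-test, 15 subjects have 99.1% power if that SD is 0.5, and 90% power if it is 0.666. Both values are carried below.

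**2. What HbA1c replaced subjects would have.** Titration can end at day 14 (3 tablets kept), day 21, or about day 28 (Visit 4). Two months, taken as 56 to 61 days, then ends at day 70-75, 77-82 or 84-89. Visits 4, 5 and 6 fall at about days 28, 56 and 84 of the 16-week treatment period.

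- Stopped during titration: usually no post-baseline HbA1c.
- Withdrawn less than 2 months after titration: 0 to 2 values, or 3 at the latest cut-offs.
- Withdrawn later without final procedures: past Visits 4 and 5, so at least 2 scheduled values.

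**3. Shift in the mean.** Assume 15 completers with mean change -0.60 (the planned effect) and k replaced subjects with mean change c. The all-dosed mean is M = (15 x (-0.60) + k x c) / (15 + k). For k = 4 and c = 0, M = -9.0 / 19 = -0.474.

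| k (share of dosed) | c = -0.60 | c = -0.30 | c = 0 | c = +0.30 |
|---|---|---|---|---|
| 2 (12%) | -0.600 | -0.565 | -0.529 | -0.494 |
| 4 (21%) | -0.600 | -0.537 | -0.474 | -0.411 |
| 6 (29%) | -0.600 | -0.514 | -0.429 | -0.343 |

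At c = 0 the completer mean overstates the reduction by 0.07, 0.13 or 0.17. At c = -0.60 the overstatement is zero.

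**4. Against the standard error.** With 15 subjects, SE = 0.5 / sqrt(15) = 0.129 or 0.666 / sqrt(15) = 0.172. The c = 0 shifts are 0.55, 0.98 and 1.33 SE in the first case, and 0.41, 0.73 and 1.00 SE in the second.

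**5. Effect on the test.** Take the all-dosed group at c = 0, with variance SD^2 + d(1 - d) x 0.6^2 and d = k / (15 + k). A one-sample t-test at the expected mean gives p between 0.0009 and 0.003 at SD 0.5, and between 0.006 and 0.013 at SD 0.67. The illustrated shift changes the estimate, not the significance.

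**6. Would a repeated-measures model alone correct it?** A simulation (400 runs, all inputs assumed) used completers at 0, -0.2, -0.4, -0.55 and -0.60 over baseline and months 1 to 4, and 4 replaced subjects with no change. The between-subject SD was 0.4 and the within-subject SD 0.3 (so an SD of change of 0.3 x sqrt(2) = 0.42), with a random-intercept model. The true all-dosed mean is -0.474; the completer mean was -0.595. The month-4 estimate was -0.594, -0.579, -0.560 or -0.542 when the replaced subjects' last HbA1c was at baseline, month 1, 2 or 3. The model recovers between nothing and about 0.05 of a shift of about 0.13.

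**The case against.** A reader might infer that the plan specifies a completer analysis and discards HbA1c from replaced subjects. The documents do not say so. No section deletes those data. The verb in section 10.2 concerns assaying, and may cover only stored research samples, since HbA1c is drawn monthly from everyone still on study. On that reading section 10.2 is silent on the HbA1c set. This stands: a completer mean is where the stated rules most naturally lead, not something the plan declares.

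The SAP is deferred and could define the set. That also stands and limits the severity. But section 10.1 requires it only before database lock, and in an open-label study outcomes can be seen before then.

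The glycaemic route out of the study is narrow: two consecutive high values after titration, then only evaluation for withdrawal. Final examinations for late withdrawals recover some endpoint data. Both are fair, but neither reaches subjects lost to intolerance or early withdrawal, and sections 9.1 and 10.2 do not say whether late withdrawals with final examinations count as completers.

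Finally, an effect among subjects who tolerate the drug is a legitimate target in a small Phase IV study with a mechanistic co-primary objective, if it is labelled as that. This is accepted. An all-dosed mixed model need not be the primary analysis.

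**Conclusion.** Section 10.2 leaves the efficacy set undefined and does not say how HbA1c from replaced subjects is used. Read with sections 3.1 and 9.1, the rules most naturally produce a completer mean in a single-arm study, and that mean overstates the HbA1c reduction if non-completers do worse.

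The size cannot be fixed from the documents, which give no dropout rate, no outcome for non-completers and no SD of change. With 15 completers at -0.60 and 2, 4 or 6 replaced subjects assumed to have no change, the overstatement is 0.07, 0.13 or 0.17 HbA1c percentage points; it is zero if they respond alike.

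Two stronger conclusions are not supported. Bias is not established, because it depends on an unknown difference between completers and non-completers. Nor does the illustration point to a false-positive result, because the all-dosed test stays significant under the assumptions shown. The point should be fixed because the remedy is cheap and the estimate is the study's main product. Confidence is moderate.

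**What to change.** Amend section 10.2 and carry the wording into the SAP before outcomes are reviewed:

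1. Assay and keep every HbA1c sample already drawn from each subject who took at least one dose, including replaced subjects.
2. Report an all-dosed HbA1c analysis beside the completer analysis, either as primary or as a pre-specified sensitivity analysis. Use the observed month 1 to 4 values, and include a version that assigns no change to non-completers, including those with no post-baseline value. A mixed model is one option, not a requirement; by itself it corrects little of the shift. State which month-4 value is used, since HbA1c is drawn at both Visit 7 and Visit 8.
3. Report the numbers dosed, withdrawn and replaced, with the reasons already recorded under section 9.1.
4. Label any completer-only result, including the mixed-meal co-primary, as an effect among subjects who tolerated and completed treatment. State whether late withdrawals with final examinations count as completers, reconciling sections 9.1 and 10.2.

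The withdrawal and replacement rules need not change. The cost is wording, plus at most a few assays on blood already drawn; no new visits or subjects are needed. The downside is that the estimate may be smaller, and that part of the sensitivity analysis rests on assigned values.

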10.3 SAMPLE SIZE

Assuming that Cycloset will cause a 0.6% reduction in HbA1c, 15 subjects would provide 90% power to detect a 0.6% decrease from a baseline HbA1c of 8.0 ±0.5% at an alpha of 0.05.

11 REGULATORY REQUIREMENTS

11.1 GOOD CLINICAL PRACTICE

This study is to be conducted according to globally accepted standards of good clinical practice (as defined in the ICH E6 Guideline for Good Clinical Practice, 1 May 1996), in agreement with the Declaration of Helsinki and in keeping with local regulations.

11.2 DELEGATION OF INVESTIGATOR DUTIES

The investigator will ensure that all persons assisting with the trial are adequately qualified, informed about the protocol, any amendments to the protocol, the study treatments, and their trial-related duties and functions.

The investigator will maintain a list of sub investigators and other appropriately qualified persons to whom he or she has delegated significant trial-related duties.

11.3 SUBJECT INFORMATION AND INFORMED CONSENT

Before being enrolled in the clinical study, subjects must consent to participate after the nature, scope, and possible consequences of the clinical study have been explained in a form understandable to them.

An informed consent document that includes information about the study will be prepared and given to the subject. This document will contain all the elements required by the ICH E6 Guideline for Good Clinical Practice and any additional elements required by local regulations. The document must be in a language understandable to the subject and must specify who informed the subject. Where required by local law, the person who informs the subject must be a physician.

After reading the informed consent document, the subject must give consent in writing. The subject's consent must be confirmed at the time of consent by the personally dated signature of the subject and by the personally dated signature of the person conducting the informed consent discussions.

If the subject is unable to read, oral presentation and explanation of the written informed consent form and information to be supplied to subjects must take place in the presence of an impartial witness. Consent must be confirmed at the time of consent orally and by the personally dated signature of the subject or by a local legally recognized alternative (e.g., the subject's thumbprint or mark). The witness and the person conducting the informed consent discussions must also sign and personally date the consent document.

A copy of the signed consent document must be given to the subject. The original signed consent document will be retained by the investigator.

"Legally authorized representative" means an individual or judicial or other body authorized under applicable law to consent on behalf of a prospective subject to the subject's participation in the procedure(s) involved in the research.

The investigator will not undertake any measures specifically required only for the clinical study until valid consent has been obtained.

It is recommended that the investigator inform the subject's primary physician about the subject's participation in the trial if the subject has a primary physician and if the subject agrees to the primary physician being informed.

11.4 CONFIDENTIALITY

Subject names will not be supplied to the sponsor. Only the subject number and subject initials will be recorded in the case report form, and if the subject name appears on any other document (e.g., laboratory report), it must be obliterated on the copy of the document to be supplied to the sponsor. Study findings stored on a computer will be stored in accordance with local data protection laws. The subjects will be informed that representatives of the sponsor, independent ethics committee (IEC)/ institutional review board (IRB), or regulatory authorities may inspect their medical records to verify the information collected, and that all personal information made available for inspection will be handled in strictest confidence and in accordance with local data protection laws.

The investigator will maintain a personal subject identification list (subject numbers with the corresponding subject names) to enable records to be identified.

11.5 PROTOCOL AMENDMENTS

Neither the investigator nor the sponsor will alter this clinical study protocol without obtaining the written agreement of the other. Once the study has started, amendments should be made only in exceptional cases. The changes then become part of the clinical study protocol.

11.6 APPROVAL OF THE CLINICAL STUDY PROTOCOL AND AMENDMENTS

Before the start of the study, the clinical study protocol, informed consent document, and any other appropriate documents will be submitted to the IEC/IRB with a cover letter or a form listing the documents submitted, their dates of issue, and the site (or region or area of jurisdiction, as applicable) for which approval is sought. If applicable, the documents will also be submitted to the authorities, in accordance with local legal requirements.

Investigational products can only be supplied to the investigator after documentation on all ethical and legal requirements for starting the study has been received by the sponsor. This documentation must also include a list of the members of the IEC/IRB and their occupation and qualifications. If the IEC/IRB will not disclose the names of the committee members, it should be asked to issue a statement confirming that the composition of the committee is in accordance with GCP. Formal approval by the IEC/IRB should preferably mention the study title, study code, study site (or region or area of jurisdiction, as applicable), amendment number where applicable, and any other documents reviewed. It must mention the date on which the decision was made and must be officially signed by a committee member.

Before the first subject is enrolled in the study, all ethical and legal requirements must be met.

The IEC/IRB and, if applicable, the authorities must be informed of all subsequent protocol amendments and administrative changes, in accordance with local legal requirements. Amendments must be evaluated to determine whether formal approval must be sought and whether the informed consent document should also be revised.

The investigator must keep a record of all communication with the IEC/IRB and, if applicable, between a coordinating investigator and the IEC/IRB. This also applies to any communication between the investigator (or coordinating investigator, if applicable) and the authorities.

11.7 ONGOING INFORMATION FOR INDEPENDENT ETHICS COMMITTEE/ INSTITUTIONAL REVIEW BOARD

Unless otherwise instructed by the IEC/IRB, the investigator must submit to the IEC/IRB:

- Information on serious or unexpected adverse events from the investigator's site, as soon as possible
- Expedited safety reports from the sponsor, as soon as possible
- · Periodic reports on the progress of the study

11.8 CLOSURE OF THE STUDY

The study must be closed at the site on completion. Furthermore, the sponsor or the investigator has the right to close this study site at any time. As far as possible, premature closure should occur after mutual consultation. Depending on local legislation, it may be necessary to inform IEC/IRB and the regulatory authorities when the study site is closed.

Study materials must be returned, disposed of or retained as directed by the sponsor.

11.9 RECORD RETENTION

The investigator must obtain approval in writing from the sponsor before destruction of any records.

Essential documents should be retained until at least 2 years after the last approval of a marketing application in an ICH region and until there are no pending or contemplated marketing applications in an ICH region, or at least 2 years have elapsed since the formal discontinuation of clinical development of the investigational product. However, because of international regulatory requirements, the sponsor may request retention for a longer period.

Essential documents include:

- Signed informed consent documents for all subjects
- Subject identification code list, screening log (if applicable) and enrollment log
- Record of all communications between the investigator and the IEC/IRB
- Composition of the IEC/IRB (or other applicable statement as described in Section 12.6)

- Record of all communications between the investigator and sponsor (or CRO)
- List of sub-investigators and other appropriately qualified persons to whom the investigator has delegated significant trial-related duties, together with their roles in the study and their signatures
- Copies of case report forms and of documentation of corrections for all subjects
- Investigational product accountability records
- · Record of any body fluids or tissue samples retained
- All other source documents (subject medical records, hospital records, laboratory records, etc.)
- All other documents as listed in section 8 of the ICH E6 Guideline for Good Clinical Practice (Essential Documents for the Conduct of a Clinical Trial)

Normally, these records will be held in the investigator's archives. If the investigator is unable to meet this obligation, he or she must ask the sponsor for permission to make alternative arrangements. Details of these arrangements should be documented.

11.10 LIABILITY AND INSURANCE

Liability and insurance provisions for this study are given in separate agreements.

11.11 FINANCIAL DISCLOSURE

Before the start of the study, the investigator will disclose to the sponsor any proprietary or financial interests he or she might hold in the investigational products or the sponsor company as outlined in the financial disclosure form provided by the sponsor. The investigator agrees to update this information in case of significant changes during the study or within one year of its completion. The investigator also agrees that, where required by law or regulation, the sponsor may submit this financial information to domestic or foreign regulatory authorities in applications for marketing authorizations.

Similar information will be provided by each sub-investigator to whom the investigator delegates significant study related responsibilities.

